2. STUDY OBJECTIVES

2.1 Primary Objective(s)

The main objective of this study is to evaluate the safety profile of the administration of porcine surfactant (poractant alfa, Curosurf®) through a less invasive method (LISA) using a thin catheter (CHF 6440) during non-invasive ventilation (NIV) (CPAP, NIPPV, BiPAP), compared to an approved conventional surfactant administration during invasive ventilation and rapid extubation, in spontaneously breathing preterm neonates with clinical signs of respiratory distress syndrome (RDS). The short-term and mid-term safety will be assessed: adverse events and adverse drug reactions occurring during overall procedure for surfactant administration, neonatal pain assessment pre- and during surfactant administration, duration of surfactant administration, incidence of BPD at 36 weeks post menstrual age (PMA), major neonatal morbidities and vital signs.

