Following direct laryngoscopy, the catheter will be introduced orally and inserted through the vocal cords into the trachea to the desired depth of 1-2 cm, the laryngoscope will be carefully removed while the catheter is secured by the fingers of the neonatologist/investigator, who will finally close the neonate's mouth. The correct position of the catheter into the trachea will be confirmed by the visualization of tip depth markings and by the tip-to-lip measurement. The thin catheter presents three different ring markings close to the tip, equal to 1, 2 and 3 cm ([Figure 1C](#)) and helpful to address the depth of insertion beyond the vocal cords. Moreover, the catheter presents markings going from 5 to 9 cm for the tip-to-lip measurement, which represents the standard method to estimate the correct position also of the ETT [\[23\]](#).

After having confirmed the correct position of the catheter into the trachea, the syringe filled with poractant alfa suspension will be connected to the Luer of the catheter and poractant alfa will be instilled over 0.5-3 minutes with careful observation of the neonate's continuous spontaneous breathing. Once the surfactant is administered, the catheter will be removed. Before removing the LISA catheter, it should be fully cleared of surfactant with some additional air. After completion of surfactant administration, ventilatory support may require transient adjustments. Airways suction should not be performed for 1 hour after surfactant instillation, unless signs of significant airway obstruction occur.

If on the first attempt the catheterization of the trachea is not possible within 30 seconds, the laryngoscope should be removed and if required neonate's recovery allowed. Then a second

attempt should be performed for a total number of 3 attempts.

Details of the procedure as well as neonate's vital signs and any occurring adverse event will be recorded according to the time points of the protocol by the team member assisting or observing the procedure.

Figure 1: CHF 6440

Figure 1A
CHF 6440 Full View

Figure 1B
Close-up on CHF 6440 Components

a) Standard Luer

b) Rounded and Soft Tip

[figure not shown]

Figure 1C
Close-up of Markings Present on CHF 6440 Shaft

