9. SAFETY ASSESSMENTS

The following variables will be used to describe the safety of the two procedures:

During procedure for surfactant administration

- Number and percentage of neonates with AEs starting during overall procedure for surfactant administration;
- Number and percentage of neonates with AEs starting during overall procedure for surfactant administration judged related to the procedure;
- Number of AEs occurring during overall procedure for surfactant administration requiring either oxygen alone or an increase in FiO₂ without the need for escalation of invasive or non-invasive ventilator support;
- Number of AEs starting during overall procedure for surfactant administration requiring administration of manual (bag and mask) pressure positive ventilation and related duration of ventilation (non- invasive ventilation);
- Number of AEs starting during overall procedures for surfactant administration requiring endotracheal intubation and related duration of intubation (invasive ventilation);
- Number of AEs starting during overall procedures for surfactant administration requiring circulatory support including administration of crystalloids;
- Number of AEs starting during overall procedures for surfactant administration requiring cardiopulmonary resuscitation including administration of cardiac massage or adrenaline.

After first administration

- Number and percentage of neonates with failed 1st attempt to insert the CHF6440/ETT;
- Number of attempts to the first successful insertion;
- Number of device misallocation (esophageal insertion);
- Number of maneuvers discontinued due to neonate's severe destabilization;
- Duration of the whole procedure (starting from the insertion of laryngoscope up to the removal of the catheter or ETT);
- Duration of surfactant administration (min);
- Heart rate (HR) and respiratory rate (RR) (0, 5, 15 and 30 min, 1 hour, 6 and 12 hours after administration);
- Systolic, diastolic, and mean blood pressure (SBP/DBP/ MBP) (15 and 30 min, 1 hour, 6 and 12 hours after administration);
- Premature Infant Pain Profile (PIPP) score [26] (end of surfactant administration).

During the study

- AEs, including incidence of major neonatal complications of prematurity (listed in [APPENDIX III](#)) and adverse drug reactions (ADRs);
- Blood pressure (SBP, DBP, MBP) at 24, 48, 72, 120 hours post-administration;

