10.4. Causality Assessment

The following “binary” decision choice will be used by the Investigator to describe the causality assessment with the study medication/device/procedure:

- Reasonable possibility of a relatedness with study medication/device/procedure
- No reasonable possibility of relatedness with study medication/device/procedure

Each AE will be evaluated for its relationship with the study drug (Poractant alfa), and also with the specific procedure for surfactant administration in both treatment groups. Moreover, for baby randomized to the LISA group, causal relationship to CHF 6440 medical device will be also assessed.

An AE will be assessed as related to the medical device (i.e. CHF 6440 catheter) if associated with its technical features or with any defect/malfunction.

An AE will be assessed as related to the procedure (i.e. LISA or intubation, surfactant administration and brief ventilation) if connected with the technique, including user difficulties in applying it.

An AE can be assessed as related to multiple choices.

The expression “reasonable possibility of relatedness” is meant to convey, in general, that there are facts (evidence) or arguments meant to suggest a causal relationship.

The Investigator will be asked to consider the following before reaching a decision on causality assessment:

- Time relationship between study drug intake/device use/procedure for administration and event’s onset;
- Medical history;
- Lack of efficacy/worsening of existing condition;
- Study treatment(s);
- Mechanism of action of the study drug/device;
- Class effects of the study drug;
- Other treatments-concomitant or previous;
- Erroneous treatment with study medication (or concomitant)/device/procedure for

- administration;
- Protocol related process.

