For pharmacovigilance purposes, all SAEs should be followed-up in order to elucidate as completely and practically as possible their nature and/or causality until resolution of all queries, clinical recovery is complete, laboratory results have returned to normal, stable condition is reached or until the subject is lost to follow-up. Follow-up may therefore continue after the subject has left the study. In this case, the follow-up will continue with no timelines for related SAEs, while for unrelated SAEs the type and extent of follow-up undertaken will be determined for each individual case and will depend upon the nature (e.g. events with poor prognosis or which do not resolve), severity and medical significance of the event.

AEs related to the procedure for surfactant administration

The procedure for surfactant administration will last from the application of the laryngoscope up to the removal of the CHF 6440 catheter in the LISA treatment group or the ETT in the comparator arm within one hour after the instillation of poractant alfa.

All AEs during procedures for surfactant administration will be carefully monitored and recorded in both arms. Specific focus will have to be paid on the following AEs:

- Obstruction of the CHF 6440 catheter or ETT;
- Bradycardia;
- Neonatal oxygen desaturation;

- Apnoea;
- Hypotension requiring treatment;
- Any episodes of cough, sneezing, choking, laryngospasm, surfactant reflux, vomiting.

A complete qualitative risk assessment has been conducted to identify and mitigate potential safety risks associated with use of CHF 6440 medical device. The results provide evidence that the benefits of using the device outweigh the residual risks and do not highlight any specific additional risk or safety issue than the ones listed above.

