12.3.5. Safety variables

Adverse Events and Neonatal Morbidities

- Number and percent of neonates reporting AEs started during procedure for surfactant administration as well as AEs started during the procedure and judged related to the procedure will be summarized by treatment group.

For LISA group, any AE assessed as related to CHF 6440 catheter will be considered procedure-related.

These events will be also summarized by treatment group based on action required, if any (i.e. supplementary oxygen or transient increase in FiO₂, manual positive pressure ventilation, endotracheal intubation, administration of, crystalloids, or cardiopulmonary resuscitation or administration of adrenaline). The duration of endotracheal intubation and positive pressure ventilation will be

summarized as well.

A subgroup analysis of AEs during procedure for surfactant administration will be performed based on the use of sedation and/or analgesia (Yes/No).

- Incidence of AEs including neonatal complications of prematurity (see [APPENDIX III](#) for complete list), related AEs (ADRs), serious AEs (SAEs) and AEs leading to death will be summarized by treatment group both in term of frequency of neonates with at least one AE and in term of frequency of AEs (number of events). All the aforementioned categories of AEs will be summarized by System organ Class (SOC) and Preferred Term (PT).
- Frequency of neonates with major neonatal morbidities at discharge or 40 weeks PMA (whichever comes first) will be summarized by treatment group.

Vital Sign

- Vital signs parameters (SBP, DBP MBP, HR and RR) will be summarized as absolute and the change from baseline (pre-procedure) by treatment group using descriptive statistics.

Pain assessment

- PIPP score will be summarized by treatment group by means of descriptive statistics.

First administration

- Number of 1st failed attempt to insert the catheter/ETT will be summarized by treatment group. Percentage of neonates with 1st failed attempt will be compared between group using the Cochran-Mantel-Haenszel adjusted for gestational age group. The CMH adjusted difference with its 95% CI will be presented.
- Number of attempts to the first successful insertion will be summarized by treatment group by means of descriptive statistics.
- Number of device misallocation (i.e., esophageal intubation) will be summarized by treatment group by means of descriptive statistics.

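### The procedural adverse event window ends at device removal, so control neonates can be observed for up to an hour longer than LISA neonates, and no summary over an equal window is planned

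*Protocol*

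**What the plan says.** Section 2.1 lists "adverse events and adverse drug reactions occurring during overall procedure for surfactant administration" first among the short- and mid-term safety assessments, and frames the objective as LISA compared with conventional administration.

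Section 10.8 defines the procedure as starting with the laryngoscope and lasting "up to the removal of the CHF 6440 catheter in the LISA treatment group or the ETT in the comparator arm within one hour" after instillation. In section 6.2.3.3, "poractant alfa will be instilled over 0.5-3 minutes with careful observation", and the LISA catheter is then removed. In section 6.2.3.4 the control neonate may be extubated immediately, ventilated manually, or connected to the ventilator with extubation due within one hour.

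Section 9 lists "Number and percentage of neonates with AEs starting during overall procedure for surfactant administration", followed by the procedure-related subset and counts by action required. Section 12.3.5 summarises "Number and percent of neonates reporting AEs started during procedure for surfactant administration" by arm and adds: "These events will be also summarized by treatment group based on action required, if any". No adjustment for length of observation is described.

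Section 9 also has a separate variable, "Duration of the whole procedure (starting from the insertion of laryngoscope up to the removal of the catheter or ETT"), which carries no one-hour limit.

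**The concern.** The event window closes on a different clock in each arm. A desaturation 20 minutes after dosing is counted in a control neonate who still has the tube in place, but not in a LISA neonate whose catheter came out minutes earlier. The two percentages sit side by side under a comparative safety objective and invite a like-for-like reading that the window does not support.

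The events at issue matter to this trial. Section 1.2 reports that desaturation, apnea, bradycardia and surfactant reflux have been seen more often during LISA than during conventional administration, and section 10.8 asks for specific attention to them. Desaturation, apnea and bradycardia need no device in place, and section 6.2.3.3 expects that ventilatory support may need transient adjustment after LISA dosing. An event just after catheter removal that needs more oxygen drops out of the procedural summary. The definition could therefore mask or offset the acute LISA signal that the protocol anticipates.

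There is also a gap in the text. Section 10.8 places tube removal within one hour of instillation, while the duration variable in section 9 ends at tube removal with no limit. Section 8 foresees controls not extubated within an hour, and no end of the event window is stated for them.

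**Working it through.** The protocol states no figure on this point, so there is nothing to reproduce. The check has three parts.

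**1. Window length implied by the text.** Section 6.2.3.3 allows 30 seconds per catheterization attempt, up to 3 attempts, and 0.5 to 3 minutes of instillation. Ignoring recovery between attempts:
- LISA, shortest: 0.5 + 0.5 = 1 minute. Longest: 3 × 0.5 + 3 = 4.5 minutes.
- Control, assuming the same front part plus 0 to 60 minutes of tube time: 1 to 64.5 minutes.

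With immediate extubation the windows are equal. With 60 minutes of tube time the control window is 64.5/4.5 = 14 times to 61/1 = 61 times as long.

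Averaged over an arm in which half the controls keep the tube for 30 minutes, the mean control window is L + 0.5 × 30, where L is the LISA window. For L of 2, 4 and 10 minutes this gives 17, 19 and 25 minutes, or ratios of 8.5, 4.8 and 2.5.

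**2. Percentage points added to controls under identical risk.** All inputs are assumptions: *a*, acute procedural risk, equal in both arms; *h*, background event hazard per minute, equal in both arms; *p*, share of controls retained on the tube after instillation; *m*, extra tube minutes.

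Added control proportion = p × (1 − a) × (1 − exp(−h × m)).

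Worked example with a = 0.30, p = 0.5, h = 0.005, m = 30: 0.5 × 0.70 × (1 − exp(−0.15)) = 0.35 × 0.139 = 0.049, or 4.9 points.

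| a | p | m (min) | h = 0.001 | h = 0.002 | h = 0.005 |
|---|---|---|---|---|---|
| 0.30 | 0 | any | 0 | 0 | 0 |
| 0.30 | 0.5 | 15 | 0.5 | 1.0 | 2.5 |
| 0.30 | 0.5 | 30 | 1.0 | 2.0 | 4.9 |
| 0.30 | 0.5 | 60 | 2.0 | 4.0 | 9.1 |
| 0.30 | 1 | 60 | 4.1 | 7.9 | 18.1 |
| 0.10 | 0.5 | 30 | 1.3 | 2.6 | 6.3 |
| 0.50 | 0.5 | 30 | 0.7 | 1.5 | 3.5 |

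With 50 controls, points divided by 2 gives neonates. The rows with a = 0.30 and half retained span about 0.3 to 4.5 neonates.

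**3. Whether another planned analysis fills the gap.**
- The overall event tables (section 12.3.5) use a common period, but it runs to the end of participation (section 10.8) and cannot isolate the first hour.
- SpO₂, FiO₂ and vital signs are taken at common times after the end of administration (section 7.1.2). They are snapshots, not event counts.
- Procedure duration is compared by arm (section 12.3.5) but is not linked to the event percentages.

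None of these gives a peri-procedural event count over equal time.

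**The case against.** The strongest defence is that tube time belongs to the control treatment. Section 10.4 describes an event as "related to the procedure (i.e. LISA or intubation, surfactant administration and brief ventilation"), so events during brief ventilation are a consequence of the strategy being compared, and the extra minutes are not bias unless the question becomes risk per minute. This stands as a reason to keep the device-in-place table. It does not make that table a like-for-like comparison, because LISA neonates are not followed over the corresponding minutes after catheter removal.

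Second, the statistical analysis plan was not available for this review and could add a common-window table from events already recorded. That is true. But the unequal window is fixed in the protocol, as are the variables built on it, so the point is not about omitted detail.

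Third, the effect is uneven across items. A control who is still intubated can hardly register an event requiring intubation or bag-and-mask ventilation, so the extra time adds little there. This also stands. It fits the claim that longer observation can only add control events, and for some items adds almost none.

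Fourth, the magnitudes are assumed. The upper hazard implies that 1 − exp(−0.3) = 26% of neonates have a new background event each hour, and nothing in the protocol supports or excludes that. No test of these events is planned, and readers will see procedure duration by arm. These points limit the consequence to a misleading descriptive comparison.

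Last, capping the event window at one hour is the natural reading of section 10.8. That is probably so, but it needs to be stated.

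**Conclusion.** The concern holds and should be fixed. As written, the protocol compares procedural adverse events over unequal time at risk on the first-listed item of its main safety objective. Under equal hazard in both arms, the difference cannot disfavour LISA. Its size depends on how many controls stay intubated, and for how long, neither of which the protocol gives. Under the stated assumptions it runs from nothing to 18.1 points, with 1.0 to 4.9 points if half of controls stay for 30 minutes and acute risk is 30%. Equal hazard with and without a tube is itself an assumption. The fault is bias in descriptive percentages, not an error in a hypothesis test. The unstated window end for controls not extubated within an hour is a smaller, separate matter of wording.

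**What to change.** - Keep the existing table as a description of each procedure, and show procedure duration by arm beside it.
- Add the same summaries (any, procedure-related, by action required) over one window defined identically in both arms and long enough to cover planned control extubation. One example is first laryngoscope insertion to 60 minutes after the end of instillation, the time zero already used in sections 7.1 and 7.1.2. If no surfactant is instilled, end the window 60 minutes after the last laryngoscope removal.
- Confirm that the time of event onset, not only the date, is captured for that period.
- Reconcile the one-hour wording in section 10.8 with the unlimited end in section 9, and state which end time the event analysis uses for controls not extubated within one hour.
- Leave the Mann-Whitney comparison of overall procedure duration as it is; instillation time is already tested separately.

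The cost is one table, one clarifying sentence and a data-capture check. No clinical rule changes. The drawback is that the common window admits background respiratory events after device removal. With a = 0.30, the expected percentage becomes 0.30 + 0.70 × (1 − exp(−60h)), which is 34.1%, 37.9% and 48.1% for h of 0.001, 0.002 and 0.005. It rises equally in both arms, so the expected difference under equal hazard is zero, but some of the acute contrast is diluted. That is why the new table should stand beside the present one and not replace it.

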Most relevant forbidden concomitant treatments	
 • Surfactant treatment prior to randomization and study treatment administration • Intratracheal administration of any other treatment (e.g. nitric oxide) prior to randomization and study treatment administration • Other investigational drugs or investigational devices under the provisions of a protocol on the same therapeutic target. See exclusion criteria #10.
Safety variables	
During procedures for surfactant administration
 
 • Number and percentage of neonates with adverse events (AEs) starting during overall procedure for surfactant administration • Number and percentage of neonates with AEs starting during overall procedure for surfactant administration and judged related to the procedure • Number of AEs starting during overall procedure for surfactant administration requiring either oxygen alone or an increase in FiO₂ without the need for escalation of invasive or non-invasive ventilator support • Number of AEs starting during overall procedure for surfactant administration requiring administration of manual (bag and mask) pressure positive ventilation and related duration of ventilation (non-invasive ventilation) • Number of AEs starting during overall procedure for surfactant administration requiring endotracheal intubation and related duration of intubation (invasive ventilation) • Number of AEs starting during overall procedures for surfactant administration requiring circulatory support including administration of crystalloids • Number of AEs starting during overall procedures for surfactant administration requiring cardiopulmonary resuscitation including administration of cardiac massage or adrenaline 
After first administration
 
 • Number and percentage of neonates with failed 1st attempt to insert the CHF 6440/ETT • Number of attempts to the first successful insertion • Number of device misallocation (i.e., esophageal insertion) • Number of maneuvers discontinued due to neonate's severe destabilization

	
 • Duration of surfactant administration (min) • Duration of the overall surfactant administration procedure (from the insertion of laryngoscope up to the removal of the catheter or ETT)

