6.2.3.4 Conventional Intubation, surfactant administration and brief ventilation

As standard control treatment, neonates spontaneously breathing and stabilized on NIV will receive surfactant via ETT using an approved method of administration, connecting the syringe filled with poractant alfa suspension to:

- a 5-French end-hole catheter inserted into the ETT
or
- the proximal end of the secondary lumen of a dual lumen ETT.

The standard ETT has markings along the side to help identifying the correct distance from the tip of the tube.

Following direct laryngoscopy, the ETT will be inserted through the vocal cords into the trachea to the desired depth. The laryngoscope will be then carefully removed. The correct ETT position into the trachea will be confirmed by the visualization of tip depth markings and by the tip-to-lip measurement. The tube position could be checked by auscultation of the chest to ensure equal aeration of both lungs, observation of chest movement synchronous with positive pressure inflation, enhancement of vital signs, absence of stomach distension while ventilation, and where possible, with the measurement of end tidal CO₂ by colorimetric system on the ETT. Once the tube position is confirmed, the ETT will be secured with adhesive tape or other ways according to the NICU policy.

After administration, manual ventilation can be continued, or the neonate can be connected to the ventilator, or the neonate can be immediately extubated and placed again on NIV. Do not suction airways for 1 hour after surfactant instillation unless signs of significant airway obstruction occur.

If connected to the ventilator, extubation should be performed within one hour after surfactant administration and then the neonate placed again on NIV.

Details of the procedure as well as neonate's vital signs and any occurring adverse event will be recorded according to the time points of the protocol by the team member assisting or observing the procedure.

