8. EFFICACY ASSESSMENTS

The following variables will be used to describe the efficacy of the two procedures:

- Percentage of neonates needing invasive mechanical ventilation (MV) in the first 72 hours of life, 28 days PNA and within 36 weeks PMA defined as follows:

ETT group

- neonates not extubated within 1 hour from initial surfactant administration and receiving MV for more than 1 hour;
- neonates extubated and re-intubated to receive MV of any duration.

LISA group

- neonates intubated to receive MV of any duration,
 - Duration of invasive ventilation (hours) in the first 72 hours of life, 28 days PNA and within 36 weeks PMA;
 - Percentage of neonates needing any intubation procedure, outside the initial surfactant administration period, in the first 72 hours of life, in the first 28 days PNA and within 36 weeks PMA;
 - SpO₂ at time 0 (study treatment administration), 5, 15, 30 minutes, at 1, 6, 12, 24, 48, 72 and 120 hours post treatment; additionally, at 28 days PNA and at 36 weeks PMA for neonates still receiving any form of respiratory support;
 - FiO₂ at time 0 (study treatment administration), 5, 15, 30 minutes, at 1, 6, 12, 24, 48, 72 and 120 hours post treatment; additionally, at 28 days PNA and at 36 weeks PMA for neonates still receiving any form of respiratory

support;

- SpO₂/FiO₂ at time 0 (study treatment administration), 5, 15, 30 minutes, at 1, 6, 12, 24, 48, 72 and 120 hours post treatment; additionally, at 28 days PNA and at 36 weeks PMA for neonates still receiving any form of respiratory support;
- Percentage of neonates needing additional surfactant doses and number of surfactant doses;
- Duration of oxygen alone supplementation (days) and any non-invasive ventilation during the study (days);
- Blood gas analysis, specifically acid-base balance parameters (i.e. pH, pCO₂, pO₂, HCO₃, BE, lactate) pre-surfactant administration (when applicable), at 1 hour, 6 hours, 24, 48 and 72 hours after study treatment.

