12. STATISTICAL METHODS

12.1. Sample Size

No primary efficacy endpoint was defined in this study since the main objective is to describe the overall safety and efficacy profile of administering poractant alfa with two different

procedures: LISA technique or conventional administration with endotracheal tubes and brief invasive ventilation. A total of 150 neonates will be randomized in the study with a ratio 2:1 to LISA arm (i.e. 100) and conventional administration arm (i.e. 50).

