- Number of maneuvers discontinued due to neonate's severe destabilization will be summarized by treatment group by means of descriptive statistics.
- Duration of surfactant administration (min) and overall procedure for surfactant administration will be compared between treatment groups by using the Mann-Whitney U- test.

Mortality and BPD

- Death/BPD incidence at 36 weeks PMA will be compared by treatment by means of CMH test, adjusting for GA group and related 95% confidence interval will be provided.

- The incidence of BPD at 36 weeks PMA will be compared by treatment as for Death/BPD incidence.
- The mortality at 36 weeks PMA and at Day 28 will be compared by treatment as for Death/BPD incidence.
- Oxygen use at Day 28 (alone and / or during any kind of MV) will be compared by treatment as for Death/BPD incidence.

Other safety variables

- Feeding and hearing status at discharge or 40 weeks PMA (whichever comes first) will be summarized by treatment group by frequency distributions.
- Weight, OFC and length at discharge home or 40 weeks PMA will be summarized by treatment group by descriptive statistics.
- Neonates needing invasive or non-invasive respiratory support at discharge home or 40 weeks PMA will be summarized by treatment group by frequency distribution
- Neonates needing respiratory medications at discharge home or 40 weeks PMA will be summarized by treatment group by frequency distribution

Health status questionnaire at 24 months (± 3 months) corrected age

(This stand-alone assessment will be analyzed and reported separately from the main phase)

- Bayley Scales of Infant Development (cognitive and language scores) will be summarized using descriptive statistics by treatment group and BSID version (III or IV).
- Vital signs and all other variables collected through the questionnaire (i.e., anthropometric measures, cerebral palsy, seizures, feeding method, functional disability and respiratory morbidity) will be summarized by treatment group by frequency distribution or descriptive statistics, as appropriate.

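### For a control neonate still intubated through the original tube after one hour, the protocol gives inconsistent ends of the procedure, and the uncapped one can widen duration and adverse-event counting in the control arm only

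*Protocol*

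**What the plan says.** Three places in the protocol describe when the procedure ends.

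- **Protocol Outline, safety variables:** "Duration of the overall surfactant administration procedure (from the insertion of laryngoscope up to the removal of the catheter or ETT". No time limit is given.
- **Section 9, after first administration:** "Duration of the whole procedure (starting from the insertion of laryngoscope up to the removal of the catheter or ETT". Again there is no limit.
- **Section 10.8, AEs related to the procedure:** it starts at laryngoscope application and lasts "up to the removal of the CHF 6440 catheter in the LISA treatment group or the ETT in the comparator arm within one hour" after poractant alfa is instilled. Nothing is said about a tube still in place at that point.

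Two other sections bear on the same neonates. Section 6.2.3.4 states an expectation: "If connected to the ventilator, extubation should be performed within one hour after surfactant administration". Section 8 provides for those who pass the hour, classing as needing invasive mechanical ventilation (MV) control "neonates not extubated within 1 hour from initial surfactant administration and receiving MV for more than 1 hour".

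The interval feeds two kinds of result. Section 9 opens with "Number and percentage of neonates with AEs starting during overall procedure for surfactant administration" and several further counts built on the same interval. Section 12.3.5 plans a test of duration: "overall procedure for surfactant administration will be compared between treatment groups by using the Mann-Whitney" U-test.

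**The concern.** A control neonate ventilated through the original tube beyond one hour has no agreed procedure end. Under Section 9 and the Outline, the whole time to tube removal is procedure, although Section 8 treats the same ventilation as an MV outcome. Under Section 10.8 the reader must infer a cut-off.

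This matters because safety is the main objective, and adverse events (AEs) during the overall procedure are the first item Section 2.1 lists. The same interval also governs the summaries by action required and the sedation subgroup in Section 12.3.5.

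Any stretching is confined to one arm. Section 6.2.3.3 has the LISA catheter removed once surfactant is given, so only the control window can lengthen. In an open-label trial that would favour LISA.

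**Working it through.** **Stated figures.** The protocol gives no figure for this point. Its sample size ("A total of 150 neonates will be randomized in the study with a ratio 2:1") is consistent: 150 × 2/3 = 100 LISA and 150 × 1/3 = 50 control. It says nothing about how many controls pass one hour.

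**The texts applied to one case.** Take a control whose first tube is removed H hours after laryngoscope insertion, with H well above 1.

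- Outline and Section 9: the procedure lasts H hours.
- Section 10.8: about one hour if the phrase is a limit; no end is given if it only describes the expected course.
- Section 8: the neonate needed invasive MV.

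If the same neonate had been extubated and later re-intubated, every wording would end the procedure at the first removal. Only unbroken ventilation through the original tube is affected.

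**Illustration of size.** All inputs here are assumptions: a share f of the 50 controls passes one hour and keeps the tube for H hours; the others take 20 min; 40% of controls have at least one procedural AE within the capped window; new AEs then start at rate r = 0.02 to 0.05 per hour. The capped time is taken as 60 min, ignoring the short interval from laryngoscope insertion to the end of instillation.

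- Mean duration, capped: (1 − f) × 20 + f × 60 min.
- Mean duration, uncapped: (1 − f) × 20 + f × 60H min.
- Added share of controls with a procedural AE: f × (1 − 0.40) × (1 − exp(−r(H − 1))).

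For f = 10% and H = 24:

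- Capped: 18 + 6 = 24 min.
- Uncapped: 18 + 144 = 162 min.
- Added AE share: 0.06 × (1 − exp(−0.46)) = 2.2 points at r = 0.02, and 0.06 × (1 − exp(−1.15)) = 4.1 points at r = 0.05.

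| f (controls) | Mean capped, min | Mean uncapped, min: H = 6 / 24 / 72 | Added AE share, points: H = 6 / 24 / 72 |
|---|---|---|---|
| 6% (3) | 22.4 | 40.4 / 105.2 / 278 | 0.3–0.8 / 1.3–2.5 / 2.7–3.5 |
| 10% (5) | 24.0 | 54 / 162 / 450 | 0.6–1.3 / 2.2–4.1 / 4.5–5.8 |
| 20% (10) | 28.0 | 88 / 304 / 880 | 1.1–2.7 / 4.4–8.2 / 9.1–11.7 |
| 30% (15) | 32.0 | 122 / 446 / 1310 | 1.7–4.0 / 6.6–12.3 / 13.6–17.5 |

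**The rank test.** It uses only the ordering of values. A control at 60 min would already rank above nearly every LISA neonate, so moving it to 24 h changes little. In a simulated example (100 LISA around 4 min, 50 controls around 15 min, 10 of them set to 60 min or to 24 h), U was 220 and the control median 15.3 min in both cases.

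**The case against.** The best defence is that Section 10.8 is the text written for procedural AEs, and it carries the hour. Section 8 uses the same boundary and Section 6.2.3.4 the same expectation, so tube time up to one hour is naturally read as procedure and later tube time as ventilation. The unlimited wording is attached to the duration variable, not to the AE variables. Laryngoscope-to-removal time is also a legitimate description of the control technique. All AEs are recorded until participation ends, ventilation dates and times are collected, and a statistical analysis plan may settle the derivation.

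Much of this stands. An implied cap in Section 10.8 is a reasonable reading, and true tube time is worth reporting. But the implied cap then conflicts with Section 9 and the Outline. The separation of the two variables is not secure either, because the Outline attaches the unlimited definition to the overall procedure, the same term the AE variables use. The problem is definitions that disagree within the protocol, not detail left to a later plan, and sites record procedural AEs under this wording.

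A reader might infer three stronger things that the documents do not support.

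- **That rescue ventilation in general becomes procedure time.** Re-intubation after extubation lies outside every wording.
- **That the planned test of duration is distorted.** It hardly moves.
- **That the control procedure will be shown as less safe than it is.** That depends on how many controls pass the hour and how the window is applied. The count restricted to events judged related to the procedure also gives partial protection.

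**Conclusion.** The inconsistency is real and worth correcting. Followed as written, the Outline and Section 9 let continued ventilation through the original tube enter the mean, SD and maximum of control procedure duration, all of which Section 12.3.1 plans to report. They can also widen the window for all AEs starting during the procedure. Both effects arise only in the control arm.

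The size cannot be fixed from the protocol. Under the stated assumptions, mean control duration is about 22 to 32 min capped and 40 to 1310 min uncapped, and the control procedural-AE share rises by 0.3 to 17.5 points. Ranges that wide show the direction and the sensitivity; they are not an expected bias. The AE figures also apply only if the AE window is read as uncapped.

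**What to change.** Reconcile the Outline, Section 9 and Section 10.8 with one counting definition for both procedural AEs and procedure duration: the procedure ends at device removal or one hour after the end of instillation, whichever is first. Count AEs that start later in the general AE analysis, and later tube time in the MV analysis. Laryngoscope-to-removal time may still be reported descriptively, with controls who meet the Section 8 MV definition identified.

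The rule uses the hour already in Sections 6.2.3.4, 8 and 10.8. It changes counting only and implies no change to when a neonate is extubated. The cost is wording in three places, plus a check that the eCRF captures the times of AE onset, end of instillation and tube removal precisely enough to apply the cut-off.
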